staining; 5) orthodontic appliances or partial removable dentures; 6) participation in other clinical trials; 7) professional prophylaxis within 3 months or tooth whitening within 6 months; and 8) known allergy to study products.

Randomization

Eligible patients were assigned computer-generated random numbers in ascending order as they were enrolled in the study by an external dentist. They were then randomly allocated to one of three groups. The external dentist responsible for randomization maintained exclusive access to the group allocation information throughout the trial. All other study personnel remained blinded to the randomization information during the study.

Intervention

Patients in test group 1 were given the Oclean Digital Visual toothbrush (2.16 N·cm torque), patients in test group 2 received the Oclean Sonic Electric toothbrush (1.96 N·cm torque), and patients in the control group were provided with the Oral-B Classic 40 soft regular manual toothbrush.

Patients received their assigned toothbrushes along with the same toothpaste. The distribution of the study products occurred at a separate location. One study member was responsible for distributing the study products, while all other study members remained unaware of group assignments throughout the study.

Patients were instructed to brush their teeth twice daily (once in the morning and once in the evening) for one minute each session, using only the provided products, while maintaining their usual diet and oral hygiene habits.

Clinical assessments

Clinical examinations were conducted at baseline, 4 weeks, and 8 weeks by a single investigator who was unaware of the type of toothbrush used by each patient. The examinations included assessments of tooth stain as well as evaluations of both soft and hard oral tissues. Tooth stain was assessed on the buccal surfaces of six maxillary anterior teeth and on both the buccal and lingual surfaces of six mandibular anterior teeth using the Lobene Stain Index[30]. Each tooth surface was divided into two regions: the gingival region and the body region. The Lobene Stain Index quantifies

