both the area and intensity of extrinsic tooth stain. The stain intensity was scored on a scale from 0 to 3, with the following criteria: 0 = no stain; 1 = light stain (yellow to light brown or gray); 2 = moderate stain (medium brown); and 3 = heavy stain (dark brown to black). Stain area was also scored on a scale from 0 to 3, based on the proportion of the tooth surface covered by stain, using these criteria: 0 = no stain detected; 1 = stain covering up to one-third of the region; 2 = stain covering more than one-third to two-thirds of the region; and 3 = stain covering more than two-thirds of the region. The composite score was calculated as the product of the stain area and intensity scores. The mean Lobene stain area, intensity, and composite scores were determined by summing the scores from all assessed regions of the tooth surfaces and dividing by the total number of regions evaluated.

A comprehensive examination of the oral soft and hard tissues was conducted to identify any abnormalities. The assessment included the soft and hard palate, oral mucosa, tongue, sublingual and submandibular regions, salivary glands, and the pharyngeal and laryngeal areas.

At each follow-up, an investigator asked patients about any adverse events during product use, including brushing discomfort, allergic reactions, and changes in oral soft tissues. General health changes related to the product were also monitored throughout the study.

After each examination session, the collected data were securely stored by a designated study facilitator. Other study personnel had no access to participant data during the study.

Statistical analysis

Statistical analyses were performed to assess differences among the three groups. Chi-square test and one-way analysis of variance (ANOVA) were utilized to compare the differences among treatment groups on gender, age and baseline Lobene stain scores. Analysis of covariance (ANCOVA), adjusted for baseline Lobene stain score as a covariate, was applied to compare inter-group differences in stain area, intensity, and composite scores at 4 and 8 weeks. Within each group, paired t-tests were used to

assess changes in Lobene stain scores between baseline and each follow-up time point (4 and 8 weeks). All tests were two-sided, with a significance threshold set at $\alpha=0.05$.

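### No primary score, visit, contrast or error-control rule is named, and six three-arm ANCOVAs are each tested at 0.05: roughly a 10–19% chance of a false positive under assumed correlations

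*Combined protocol and SAP*

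**What the plan says.** The Statistical analysis section states that ANCOVA, adjusted for the baseline score, "was applied to compare inter-group differences in stain area, intensity, and composite scores at 4 and 8 weeks". It continues "Within each group, paired t-tests were used to" examine change from baseline to each follow-up. The only decision rule is "All tests were two-sided, with a significance threshold set at" 0.05, and it covers every test.

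The Clinical assessments section makes the three scores interdependent: "The composite score was calculated as the product of the stain area and intensity scores".

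No section calls any score, visit or comparison primary. The Sample size calculation uses the area score without calling it primary and without giving a visit. Eligibility in Study population uses the composite. The Intervention section labels two sonic arms as test groups, while "patients in the control group were provided with the Oral-B Classic 40 soft regular manual toothbrush", but no sonic-versus-manual contrast or post-hoc method is specified.

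**The concern.** The question is whether a sonic brush removes more stain than a manual brush. Under the plan as written, any of six score-by-visit results could be presented as the answer once the data are known, each judged as if it were the only test. The nominal 5% then does not describe the chance of a false efficacy finding.

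Two further gaps bear on the same claim. A significant three-group ANCOVA says that the arms differ somewhere, not which brush differs from which. The paired t-tests compare each arm with its own baseline. Participants were selected for a mean composite above 1, and "Patients received their assigned toothbrushes along with the same toothpaste", so a fall common to all arms can make these tests significant with no difference between brushes.

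**Working it through.** **Inputs from the document.** Three arms; 40 per arm at baseline; 10% attrition; area-score SD 0.5; two-sided 0.05 per test; three scores; two follow-up visits; composite equal to area times intensity.

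**Counts.** Between-group tests: 3 scores × 2 visits = 6. Within-group tests: 3 arms × 3 scores × 2 visits = 18, if all three scores are tested.

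**The plan's own figure.** Evaluable per arm: 40 × 0.9 = 36. Detectable difference for one pairwise comparison at 80% power: √[2 × (1.96 + 0.84)² × 0.5² / 36] ≈ 0.33 (0.335 using the t distribution). A 20% difference of that size implies a reference mean area score of about 0.33 / 0.20 = 1.65. The document gives no reference mean (1.5 would give 49 per group and 2.0 would give 28), so the 40 can be neither confirmed nor refuted. The calculation covers one comparison at 0.05, with no allowance for multiple tests.

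**Simple reference values.** Six independent tests: 1 − 0.95⁶ = 26.5%. Bonferroni bound: 6 × 0.05 = 30%.

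**Simulation with the product structure.** No true brush difference, 36 per arm, each score adjusted for its own baseline (error df 104), 20,000 trials per setting. Assumed: area mean 1.6, SD 0.5; intensity mean 1.3, SD 0.4. The document gives no correlations, so all of them are assumed too.

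| Area–intensity / week 4–week 8 / baseline correlation | Any of 6 tests | Any of 3 at week 8 |
|---|---|---|
| 0 / 0 / 0 | 22.5% | 11.7% |
| 0.5 / 0.5 / 0.5 | 18.7% | 10.1% |
| 0.7 / 0.7 / 0.7 | 16.7% | 9.1% |
| 0.9 / 0.8 / 0.7 | 13.6% | 7.9% |
| 0.95 / 0.95 / 0.7 | 10.5% | 7.4% |
| 0.95 / 0.95 / 0.5 | 9.9% | 7.4% |

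A single ANCOVA (area, week 8) gives 4.8–5.2%, as it should. A separate simulation with slightly different means gives 19.2% at 0.5, 22.2% at independence, and 13.4% when all correlations, including baseline, are 0.95. A negative area–intensity correlation of −0.5 gives about 23–24%.

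**Region-level check.** Scored surfaces are buccal on six upper teeth and "on both the buccal and lingual surfaces of six mandibular anterior teeth": (6 + 12) × 2 regions = 36. Unstained regions score zero on both scales (for area, "0 = no stain detected"), and the composite is averaged over regions. Over 18 assumed settings, at least one of six tests is falsely significant in 16–22% of trials. Correlations here are set at a latent level, and the eligibility cut is applied to the 36 anterior regions, so this is a plausibility check and not a like-for-like comparison. It suggests that the 10% end of the range is the optimistic end.

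**If contrasts are read instead of omnibus tests.** Unadjusted sonic-versus-manual contrasts over all scores and visits: about 17–31% at correlations of 0.5–0.95, and 37% at independence. For one score at one visit, two independent contrasts would give 1 − 0.95² = 9.75%; sharing the manual arm brings this to about 9%.

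**The case against.** Sizing on area hints at a main score, and the trial's 8-week length hints at a main visit. Both hints are fair, but neither is a designation: the eight weeks describe duration, and eligibility rests on a different score. Naming the visit alone would still leave 7–10%.

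The trial is registered, and the registry record is not part of this document. A primary outcome may be listed there. The point is therefore that none is named here, in the text that sets out the analysis.

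The percentages rest on assumed correlations. That stands. A reader might take the 22–23% at independence as a ceiling. It is not: it is one setting, for omnibus tests only, with the composite built as a product.

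A reader might also infer that the paired t-tests are meant to show that a sonic brush beats the manual brush. The document does not say so; it uses them only to assess change within each group. How often they would mislead depends on the size of a common fall, which the document does not give, so no figure is attached to them. What remains is that their role is unstated.

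Nor does the text show that any result was picked after the fact. It leaves that open.

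**Conclusion.** The concern holds for this document. Six omnibus tests at 0.05 with no primary endpoint or error-control rule carry about a 10–19% chance of at least one false positive at assumed correlations of 0.5–0.95, two to four times the nominal 5%, and about 22% at independence. This assumes no true brush difference, 36 evaluable per arm and a product composite, and it is not an upper bound.

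Naming one score and one visit restores 5% for the omnibus test only. If both sonic-versus-manual contrasts are then read unadjusted, the figure is about 9%, so naming an endpoint without a rule for the two contrasts is not enough.

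**What to change.** - Name one primary score and visit. Week-8 mean area score is consistent with the sizing score and the trial's duration. If composite is preferred, redo the sample-size statement for it.
- Make each sonic brush versus manual, from the baseline-adjusted ANCOVA with 95% confidence intervals, the two primary contrasts.
- State one error-control rule: Dunnett, Holm, a fixed order, or a gate on the three-group test.
- Label week 4, the other two scores, sonic-versus-sonic and the paired t-tests secondary or exploratory. Base no between-brush claim on within-group tests.
- The document is dated January 2022 but describes conduct from March to July 2022 in the past tense. If outcome data had been seen when the choice is made, disclose it as post hoc and report all six results with adjusted p-values.

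**Cost.** Wording, and some power per contrast. At an assumed difference of 0.33, 36 per arm and a residual SD of 0.5, power for one contrast falls from about 79% to 71% (Dunnett), 71–75% (Holm) or 68–75% (gate); the ranges span the other sonic brush having half to full effect. The first contrast in a fixed order loses nothing. The 0.33 is back-solved and not stated in the plan, so power should be restated under the chosen rule. No extra enrolment is proposed. Some secondary results would no longer be called significant.
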